9.6. Early Termination

Subjects who discontinue the study prior to the end of the 24-week Double-Blind Treatment Period or the 28-week Extension Treatment Period (Week 52) will return to the study site for an ET Visit. The ET Visit should occur within 7 days of last dose and before initiation of any new treatments.

Site staff will work with subjects who withdraw early to obtain as much follow-up data as possible, including an EGD, if not done within 4 weeks, and PFTs and ophthalmic and OCT testing. If a subject discontinues due to pregnancy, they may not be required to complete the EGD and biopsy.

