10.6.5. Pulmonary Function Test

PFTs will be performed according to the Schedules of Assessments ([Appendix 1](#); [Table 7](#) and [Table 8](#)). Where locally available, diffusing capacity of the lungs for carbon monoxide (DLCO) measurements will also be performed (sites where DLCO is not available should consult the Sponsor or Sponsor's delegate). Because carbon monoxide binds readily to hemoglobin, the diffusion capacity needs to be corrected for hemoglobin in order to reflect an altered lung gas transport rather than altered hemoglobin. All DLCO values will be corrected for hemoglobin concentration (ie, hemoglobin-adjusted diffusion capacity) in the study.

PFTs and DLCO (or other acceptable pulmonary function methods) will be conducted in all subjects in a manner consistent with the American Thoracic Society/European Respiratory Society guidelines for standardization of spirometry and single breath determination of carbon monoxide uptake in the lung [55-57]. Concern has been raised that pulmonary function testing could represent a potential avenue for COVID-19 transmission due to the congregation of patients with lung disease and because of the potential for coughing and droplet formation surrounding pulmonary function testing procedures. Refer to [Appendix 11](#) for modifications in the event that COVID-19 or similar PHE-related restrictions limit the capacity to perform non-essential PFTs.

Patient respiratory history will be collected at the Screening Visit, and any condition that might affect the outcome of PFT, including infection, respiratory symptoms, occupational exposures (including asbestos) and cigarette smoking, will be collected before every PFT and recorded in the eCRF. Furthermore, any issues with patient effort or compliance with the test procedure should be explicitly recorded in the eCRF. This information is important to determine whether PFT abnormalities may be the result of poor effort or compliance with test procedure. Smoking status (including ecigarettes) will be collected and recorded in the eCRF each time a PFT assessment is conducted.

Subjects reporting any respiratory symptoms (eg, dyspnea, shortness of breath, chest tightness, or wheezing) should be seen at an unscheduled visit for clinical assessment and full PFT assessment, preferably on the same day.

Additional guidance on clinical monitoring of pulmonary function is provided in [Section 10.6.7.5](#).

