 - ^g Safety 12-lead ECGs will be performed with the subject in the supine position prior to blood sample collection and after vital signs are measured at Screening and prior to randomization on Week 0/Day 1 (Baseline), and 4 hours (± 15 minutes) after dosing on Week 0/Day 1. At the Week 24 visit, vital signs should be measured first, followed by ECGs, predose PK sample collection, study drug dosing at the study site, and first-dose cardiac monitoring for subjects continuing in the Extension Treatment Period.
 - ^h Complete physical examination (including assessments of the skin, head, eyes, ears, nose, throat, thyroid, lungs, heart, abdomen, back, lymph nodes, extremities, body weight, and height [height collected at Week 0/Day 1 Visit only]) should be performed at Week 0/Day 1 and the ET visit.
 - ⁱ PFTs include FEV₁ and FVC measurements. Where locally available, DLCO measurements will also be performed (sites where DLCO is not available should consult the Sponsor or Sponsor's delegate). If Week 24 or ET result is abnormal, then testing should be repeated as soon as able. Post-screening PFTs may be performed within 7 days of the study visit. Details regarding additional PFTs are provided in Section 10.6.5.
 - ^j Scheduled non-screening ophthalmoscopy with OCT may be performed within 7 days of the study visit. Screening ophthalmoscopy with OCT is to be conducted with subjects' pupils dilated (Section 10.6.6).
 - ^k Only for women of child-bearing potential. Serum β -hCG test required at screening. On Day 1, urine pregnancy test must be performed and negative test result verified prior to dosing. Monthly urine pregnancy test either at home or at the study site at all other visits. Visual inspection of the test result via videoconferencing for virtual assessment is recommended. If at any point there is a positive urine β -hCG test, the subject will have study treatment interrupted and a serum sample submitted to the central laboratory for β -hCG testing (Section 10.6.9).
 - ^l Clinical laboratory tests will include serum chemistry, CBC with differentials, and coagulation. Screening samples should be obtained, and results must be available and reviewed prior to the first dose of study treatment. On other study visits, samples should be obtained prior to the daily dosing. Refer to Section 10.6.4.

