6.3. RETESTS, UNSCHEDULED VISITS, AND EARLY TERMINATION DATA

For by-visit analyses and summaries, efficacy, safety, health-related quality of life, and CCI (including scheduled, retests, unscheduled, and early termination) will be assigned to visits after the application of the windowing conventions described in Section 6.4. All measurements will be considered in summaries of abnormalities or worst-case values post-Baseline.

The visit windowing will be applied before missing data are imputed.

Listings will include scheduled, unscheduled, retest, and early discontinuation data.

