6.4. WINDOWING CONVENTIONS

All scheduled study visits are defined relative to Study Day 1, the date of first dose. Scheduled visit windows are defined in Appendix 1 of the protocol. A windowing convention will be used to determine the analysis visit value for a given measurement and will be applicable for all by-visit summaries and analyses for efficacy and safety data. See Table 3 below for specific visit windows.

Visit Windows for Efficacy and Safety Analyses

For all efficacy (except for DSQ total score), CCI health-related quality of life, safety labs and vital signs.	
Scheduled Study Visit (Protocol Scheduled Day)	Analysis Visit Window (Study Day)
Baseline (Double-Blind Treatment Period)	≤ 1 , in addition to Study Day ≤ 1 , a measurement also needs to fulfill the baseline criteria identified in Section 6.2 in order to be considered as baseline measurement
Week 0 (Day 1)	1
Week 2 (Day 15 \pm 3)	2 to 22
Week 4 (Day 29 \pm 3)	23 to 43
Week 8 (Day 57 \pm 5)	44 to 71
Week 12 (Day 85 \pm 5)	72 to 99
Week 16 (Day 113 \pm 5)	100 to 127
Week 20 (Day 141 \pm 5)	128 to 155
Week 24 (Day 169 \pm 5)	156 to 183
Week 28 (Day 197 \pm 7)	184 to 211
Week 32 (Day 225 \pm 7)	212 to 274
Week 46 (Day 323 \pm 7)	275 to 344
Week 52 (Day 365 \pm 7)	> 344

DSQ total score will be calculated every 2 weeks (week 0, 2, 4, 6, 8, 10, etc.) based on the scheduled study day starting on Day 1 For example, DSQ total score for Week 2, 4 and 6 will be calculated on Day 15, 29 and 43, respectively. .

For ECGs, OCT, and PFT.

Scheduled Study Visit (Protocol Scheduled Day)	Analysis Visit Window (Study Day)
Baseline (Double-Blind Treatment Period)	≤ 1
Week 0 (Day 1)	1
Week 24 (Day 169 ± 5)	71 to 267
Week 52 (Day 365 ± 7)	> 267

Windowing will be applied prior to any missing data calculations. The measurement that meets the Baseline criteria described in Section 6.2 will be labeled as “Baseline”. Unscheduled or Screening visits that occurred before the Baseline visit will not be assigned an analysis visit. The early discontinuation visit will be eligible for allocation to an analysis visit. The 2- and 4-Week Follow-Up visits will not be included in the visit windows and will be summarized separately without any window applied.

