If one or more results for a variable are assigned to the same analysis visit, the result with the date closest to the protocol scheduled day will be used in the analysis. If two measurements in the same analysis visit window are equidistant from the protocol scheduled study day, the earlier measurement will be used in the analysis. If multiple assessments are available on the same day, then the average of the assessment will be used in the analysis, except for laboratory and ECG data where the assessment at the earliest time of the same day will be used. If both central and local assessments of the same lab test are available on the same day, the central result will take precedence over the local result. If both central and local assessments of the same ECG test are available on the same day, the assessment of clinical significance by local reader will take precedence over the determination by a central reader.

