18.8. OTHER SAFETY ASSESSMENTS

18.8.1. PULMONARY FUNCTION TESTS

The following pulmonary function test (PFT) measurements (actual and % Predicted) will be reported for this study:

- Forced Expiratory Volume at 1 second (FEV1)
- Forced Vital Capacity (FVC)
- Total Lung Capacity (TLC)
- FEV1/FVC
- Forced Expiratory Flow (FEF) 25-75
- Diffusing Capacity of the Lungs for Carbon Monoxide (DLCO) (if available)

The following summaries will be provided for PFT data:

- Value and change from Baseline by visit
- Incidence of markedly abnormal values by visit

All PFT data will be listed. A listing in subjects who ever reported an abnormality in PFT will also be provided, including a flag for whether markedly abnormal criterion is also met.

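### PFT and OCT results on Study Days 2 to 70 have no analysis visit, so they cannot enter the by-visit change tables, and SAP 6.3 conflicts with 6.4/18.8.1 on whether such PFTs count as markedly abnormal

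*SAP*

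**What the plan says.** SAP 18.8.1 names two PFT summaries, both organised by visit. One is value and change from Baseline; the other is "Incidence of markedly abnormal values by visit". It also promises a listing of all PFT data and a listing of subjects with any PFT abnormality, flagged for the markedly abnormal criterion. SAP 18.8.2 defines markedly abnormal as below 50% for percent-predicted FEV1, FVC and FEV1/FVC. It separately defines potentially important values as a fall from Baseline of more than 20% in FEV1, FVC or DLCO. SAP 18.8.3 plans OCT summaries by visit only.

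SAP 6.4 applies its windows to every by-visit safety summary. ECG, OCT and PFT share one window table: Baseline (Day 1 or earlier), Week 0 (Day 1), Week 24 (Days 71 to 267) and Week 52 (after Day 267). The section adds: "The early discontinuation visit will be eligible for allocation to an analysis visit". It also says: "The 2- and 4-Week Follow-Up visits will not be included in the visit windows"; those visits are shown separately. Where several results share a window, "the result with the date closest to the protocol scheduled day will be used in the analysis".

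SAP 6.3 states: "All measurements will be considered in summaries of abnormalities or worst-case values post-Baseline".

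The protocol generates tests between the scheduled ones. Under 10.6.5, subjects with respiratory symptoms "should be seen at an unscheduled visit for clinical assessment and full PFT assessment, preferably on the same day". Under 9.6, sites are to collect as much follow-up as possible from early terminators, "including an EGD, if not done within 4 weeks, and PFTs and ophthalmic and OCT testing". Section 10.6.7.6 calls for unscheduled eye examinations, including OCT, after visual complaints.

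**The concern.** A PFT or OCT done after Day 1 and before Day 71 belongs to no analysis visit, and every PFT and OCT summary is laid out by visit. The tests done in that span are mostly not routine: they come from subjects who stop early or report symptoms. SAP 6.4 plainly means early discontinuation data to be usable, but before Day 71 it gives these two assessments no visit to be allocated to.

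Pulmonary events and macular edema are adverse events of special interest, and choosing a dose on efficacy and safety is a primary objective. Take a subject who reports dyspnea on Day 40, has a low FEV1 and stops. That subject contributes no on-treatment value to the change table, while one who tolerates the drug to Week 24 does. If early stopping for breathing problems differs between arms, the change table describes a selected group in each arm. The 4-Week Follow-Up PFT does not replace the missing value, because it is taken off drug and summarised apart from the windows.

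**Working it through.** **Inputs.** Windows and selection rules: SAP 6.3 and 6.4. Week 24 = Day 169 ± 5 and Week 52 = Day 365: Protocol Appendix 1. The footnote to that schedule allows a margin: "Post-screening PFTs may be performed within 7 days of the study visit". Early-termination (ET) visit within 7 days of last dose: Protocol 9.6. Planned size: 96. PFT criteria: SAP 18.8.2. Entry limit of 70% predicted for FEV1 and FVC: exclusion criterion 18.

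1. **Reproduce the plan's window.** Half the distance between the scheduled tests is (365 − 169)/2 = 98 days. Then 169 − 98 = 71 and 169 + 98 = 267, which are the printed bounds. The lower bound mirrors the upper one and does not reach back to Day 2.

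2. **Size of the gap.** Days 2 to 70 number 70 − 2 + 1 = 69. Double-blind days after Day 1 number 169 − 2 + 1 = 168. Share: 69/168 = 41.1%. The general window table in the same section (efficacy, labs, vital signs) runs without a break from Day 2 and leaves 0 days uncovered.

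3. **Each output against a Day 40 result.**
   - PFT value/change and OCT foveal thickness/change, by visit: there is no visit, so the result is excluded. SAP 6.3 does not help, because these are not summaries of abnormalities or worst-case values.
   - Markedly abnormal PFT incidence, by visit: 6.3 says the result counts; 6.4 and the layout in 18.8.1 give it no row. This is a conflict, not a clear exclusion.
   - Falls of more than 20%: 18.8.2 says they will be identified, but 18.8.1 names no table or listing flag for them, on any day.

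4. **Subjects who stay to Week 24.** The scheduled Week 24 PFT can fall from 164 − 7 = Day 157 to 174 + 7 = Day 181, at most 12 days from Day 169. Days 156 and 182 are 13 days away. So an unscheduled PFT on Days 71 to 156 or Days 182 to 267 always loses under the closest-day rule. One on Days 157 to 181 may win. This is ordinary selection within a window, not a missing window.

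5. **Early terminators affected (assumed rates).** Let d be the share stopping by Week 24 at a constant hazard. The expected number whose last dose is by day t is 96 × [1 − (1 − d)^(t/168)]. Using t = 63 allows the full 7-day lag to the ET visit; t = 70 allows none.

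| d | t = 63 | t = 70 |
|---|---|---|
| 5% | 1.8 | 2.0 |
| 10% | 3.7 | 4.1 |
| 20% | 7.7 | 8.5 |
| 30% | 12.0 | 13.3 |

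6. **Which criterion is the sensitive one.** A subject entering at 70% predicted who falls 20% is at 0.8 × 70 = 56%, still above 50%. To be markedly abnormal that subject must lose more than (70 − 50)/70 = 28.6%; one entering at 100% must lose more than half. For FEV1 and FVC, the criterion without a named summary is therefore met first. DLCO has no markedly abnormal criterion at all.

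**The case against.** The strongest reply is SAP 6.3. It follows directly on the rule for unscheduled and early-termination data, and incidence of markedly abnormal values is a summary of abnormalities. A reader might infer from the windows that a Day 2 to 70 PFT enters no by-arm PFT table at all. The documents do not support that: on 6.3 such a test should count as abnormal if it qualifies, and what is missing is a row to put it in. This stands, and it limits the certain exclusion to the change tables.

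Second, the information is tabulated by arm elsewhere. Adverse events leading to discontinuation are summarised. Airflow obstruction and decreased gas exchange are special-interest subcategories, with exposure-adjusted rates and 95% intervals. SAP 18.2.6 has spirometry reviewed for cases that investigators missed. All PFT and OCT results are listed. This also stands, though event counts do not show measured decline and listings are not a by-arm summary.

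Third, by-visit tables are the SAP's usual layout. The any-time row for labs covers only lymphocytes and neutrophils, and the worst-case ECG shift covers only the investigator's overall interpretation. So PFT is not singled out. But the ECG shares the same windows and has at least one output free of them; PFT and OCT have none.

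Fourth, few early values may fall below 50% predicted given the entry limit. That is fair for the markedly abnormal table. It strengthens the case for tabulating the 20% falls.

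Finally, SAP section 1 lets table shells be updated where they do not conflict with the SAP. An any-time abnormality row could be added there in line with 6.3, and the shells, a separate file not available here, may already have one. The SAP text should still settle the conflict.

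**Conclusion.** The point holds within limits. PFT and OCT results on Days 2 to 70 (69 of 168 days, 41%) cannot enter the by-visit change tables. For markedly abnormal PFTs, SAP 6.3 conflicts with 6.4 and 18.8.1, and a programmer would have to choose. The 20% falls have no named summary.

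The window arithmetic rests on the documents alone. The number of subjects affected does not: about 4 to 8 of 96 assumes that 10% to 20% stop by Week 24 at a constant rate and that all attend the ET test. The range is about 2 to 13 for 5% to 30%. How many real lung-function falls would go untabulated cannot be derived from the documents.

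Two stronger inferences should be resisted. A reader might conclude that every PFT on Days 170 to 267 is displaced by the Week 24 test; only Days 182 to 267 always lose to a scheduled one. A reader might also conclude that the safety data are lost or the dose choice will be wrong. The adverse event tables, the spirometry review and the listings keep the signal visible, so the effect is confined to the by-arm PFT and OCT summaries. The change is worth making because it is cheap and uses data already collected.

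**What to change.** In SAP 18.8.1, add a summary by treatment group and period of the number and percentage of subjects with (a) a markedly abnormal value and (b) a fall from Baseline of more than 20% in FEV1, FVC or DLCO, at any time on treatment through the ET visit. Use all scheduled, unscheduled, repeat and ET tests. The denominator is subjects with a Baseline and at least one such value. This carries out SAP 6.3 and gives the 18.8.2 criteria a table.

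Add a last-on-treatment row to the PFT and OCT change tables, so that subjects who stop before Day 71 contribute their final on-treatment value. Keep Day 71 as the lower bound for Week 24: moving it to Day 2 would close the gap, but only by labelling a test from the first weeks as Week 24.

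The cost is a short addition to the SAP and a few table rows, with no new data collection. DLCO rows remain subject to the 50-subject minimum in SAP 18.8.3.

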18.8.2. PFT MARKEDLY ABNORMAL CRITERIA

Markedly abnormal quantitative PFT measurements will be identified in accordance with the following predefined markedly abnormal criteria:

- % Predicted FEV1 < 50%
- % Predicted FVC < 50%
- % Predicted FEV1/FVC ratio < 50%

Potentially important PFT measurements will also be identified using the criteria below:

- Decrease from Baseline > 20% in FEV1, ie, percent change from Baseline < -20%
- Decrease from Baseline > 20% in FVC, ie, percent change from Baseline < -20%
- Decrease from Baseline > 20% in DLCO, ie, percent change from Baseline < -20%

18.8.3. OPHTHALMOSCOPY AND OPTICAL COHERENCE TOMOGRAPHY (OCT)

The following summaries will be provided for ophthalmoscopy and OCT data:

- Values and change from Baseline in central foveal thickness by visit
- Categorical result in ophthalmoscopy with OCT parameters by visit (the categories are listed on the eCRF)
- Only PFT and OCT assessments completed by 50 or more subjects in the SAF will be presented in the summaries.

A listing of all ophthalmoscopy and OCT assessments will be provided. A listing of subjects who ever reported an abnormality in OCT will also be provided.

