Study Design: 
This Phase 2, randomized, double-blind, multi-center study will evaluate the efficacy, safety, and pharmacokinetics (PK) of etrasimod compared with placebo in adults with active EoE. The study will consist of a Screening Period of up to 35 days, 24 weeks of double-blind treatment (Double-Blind Treatment Period), 28 weeks of active extended treatment (Extension Treatment Period), and 4 weeks of follow-up (Safety Follow-Up Period) for a total study duration of up to 61 weeks.
 
Eligible subjects will be randomized in a double-blind fashion (3:3:2 ratio) to etrasimod 1 mg, etrasimod 2 mg, or matching placebo once daily. Randomization will be stratified by baseline history of esophageal dilation (yes/no) and concurrent proton pump inhibitor (PPI) therapy (yes/no).
 
All subjects who complete the Double-Blind Treatment Period and meet eligibility criteria for the Extension Treatment Period may enter the Extension Treatment Period. Subjects who were in the etrasimod 1 mg or etrasimod 2 mg groups in the Double-Blind Treatment Period will continue the same etrasimod dose in the Extension Treatment Period. Subjects who were in the placebo group during the Double-Blind Treatment Period will be re-randomized (1:1 ratio) to etrasimod 1 mg or etrasimod 2 mg at entry into the Extension Treatment Period.
 
Subjects will have follow-up visits at 2 and 4 weeks after the last dose of study treatment after Week 52 or the Early Termination (ET) Visit.

Number of Subjects (planned):

Approximately 96 subjects are planned to be enrolled.

Eligibility Criteria for the Double-Blind Treatment Period:

Key Inclusion Criteria (Full Inclusion Criteria Are Provided in the Protocol)

- Men or women between 18 and 65 years of age at the time of informed consent (IC)
- Have an EoE diagnosis prior to screening and histologically active disease with an esophageal peak eosinophil count (PEC) of ≥ 15 eosinophils (eos)/high power field (hpf) (~ 60 eos/mm²) from any level (proximal, mid, or distal) of the esophagus at the Screening esophagogastroduodenoscopy (EGD)
- Have dysphagia, defined as solid food going down slowly or getting stuck in the throat with an average frequency of ≥ 2 episodes per week over 2 weeks (as documented using the Dysphagia Symptom Questionnaire (DSQ) during the Screening period)

Key Exclusion Criteria (Full Exclusion Criteria Are Provided in the Protocol)

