3. STUDY DESIGN

3.1. GENERAL DESCRIPTION

[figure not shown]
This Phase 2 randomized, double-blind, multi-center study will evaluate the efficacy, safety, and PK of etrasimod compared with placebo for 24 weeks in adults with active EoE.

The study will consist of a Screening Period of up to 35 days, 24 weeks of double-blind treatment (Double-Blind Treatment Period), 28 weeks of active extended treatment (Extension Treatment Period), and 4 weeks of follow-up (Safety Follow-Up Period) for a total study duration of up to 61 weeks. Approximately 96 subjects were planned to be enrolled.

Eligible subjects will be randomized in a double-blinded fashion (3:3:2 ratio) to etrasimod 1 mg, etrasimod 2 mg, or matching placebo once daily. Randomization will be stratified by baseline history of esophageal dilation (yes/no) and concurrent proton pump inhibitor (PPI) therapy (yes/no).

All subjects who complete the Double-Blind Treatment Period and meet eligibility criteria for the Extension Treatment Period may enter the Extension Treatment Period. Subjects who were in the etrasimod 1 mg or etrasimod 2 mg groups in the Double-Blind Treatment Period will continue the same etrasimod dose in the Extension Treatment Period. Subjects who were in the placebo group during the Double-Blind Treatment Period will be re-randomized (1:1 ratio) to etrasimod 1 mg or etrasimod 2 mg at entry into the Extension Treatment Period.

Subjects will have follow-up visits at 2 and 4 weeks after the last dose of study treatment after Week 52 or the Early Termination (ET) visit.

Figure 1: Study Design

*Esophagogastroduodenoscopy

EoE, eosinophilic esophagitis; ETR, etrasimod; F/U, follow-up; PBO, placebo.

Numbers preceded by colons represent the randomization ratio.

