18.2.6. TEAEs OF SPECIAL INTEREST

Categories of Targeted Medical Events (TMEs) and a list of preferred terms associated with these TME categories were developed based on the mechanism of action of etrasimod, prior experience with other agents acting via a similar mechanism, and disease-specific clinical judgment. In addition, where standard testing has been implemented to screen for potential AEs (eg, electrocardiograms, spirometry, serum transaminases, etc.), the relevant data will be reviewed to identify potential cases of AESI that investigators may not have identified and to provide quantitative data for AESIs. The proposed candidate terms will be reviewed to identify which events reflect AESI.

TEAEs of special interest will be summarized by category, subcategory, and PT by descending frequency by treatment group. Categories and subcategories of TEAEs of special interest are the following:

- Cardiovascular Events
 - Bradycardia
 - AV conduction delay
 - Hypertension
- Infections
 - Severe infections
 - Opportunistic infections (Narrow)
 - Herpes simplex and herpes zoster
- Macular Edema
- Pulmonary Disorders
 - Airflow obstruction (forced expiratory volume in 1 second [FEV₁], forced vital capacity [FVC])
 - Decrease gas exchange (diffusing capacity of the lungs for carbon monoxide [DLCO])
- Liver Injury
 - Liver transaminases elevation
 - Bilirubin elevation
 - Elevated BP
- Posterior reversible encephalopathy syndrome (PRES)
- Malignancies

For the TEAE of special interest, the Exposure-adjusted incidence rate (EAIR) will also be provided for the following group based on the subject in Safety Set in Double-Blinded Treatment Period

Group 1: Subjects who take etrasimod 2 mg anytime during the course of study. This includes the subjects who

- receive the etrasimod 2 mg in Double-Blind Treatment period and continue receiving Etrasimod 2 mg in Extension Treatment period, or
- receive the etrasimod 2 mg in Double-Blind Treatment period and discontinue early without entering Extension Treatment period, or
- receive the placebo in Double-Blind Treatment period and receive etrasimod 2 mg in Extension Treatment period

Group 2: Subjects who take etrasimod 1 mg anytime during the course of study. This includes the subjects who

- Subjects who take etrasimod 1 mg anytime during the course of study. This includes the subjects who

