If both central and local assessments of total bilirubin are available on the same day, the central result will take precedence over the local result in the eDISH plot. If the maximum AST/ALT/GGT assessment occurs at two different dates, the assessment with the higher accompanying Bilirubin value will be used. Two versions of the eDISH plots will be presented, with one showing values as multiples of upper limit of normal, and the other one showing values as multiples of upper limit of normal, or subject's baseline, whichever is higher.

Only laboratory tests completed by 50 or more subjects in the SAF will be presented in the summaries. All laboratory tests will be listed.

Subject's laboratory assessments at all timepoints will be listed in chronological order. Values outside of the laboratory reference range will be flagged. Values obtained from local laboratory will be flagged. Listing of lymphocytes and neutrophils over time in subjects ever with lymphocytes $<0.5 \times 10^9/L$ or neutrophils $< 1 \times 10^9/L$ will also be provided.

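### The SAP's 50-subject limit on safety summaries can drop the planned by-arm DLCO summary, the quantitative measure it names for a gas-exchange event of special interest

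*SAP*

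**What the plan says.** The limit appears twice. SAP 18.8.3, the ophthalmoscopy and OCT section, says: "Only PFT and OCT assessments completed by 50 or more subjects in the SAF will be presented in the summaries". SAP 18.4.1 says: "Only laboratory tests completed by 50 or more subjects in the SAF will be presented in the summaries". Neither gives a reason, and neither exempts measures tied to events of special interest. The pulmonary limit sits under the OCT heading, not in the PFT section.

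SAP 18.8.1 plans two PFT summaries: value and change from Baseline by visit, and incidence of markedly abnormal values by visit. DLCO is one of the listed parameters, marked as conditional on availability. Protocol 10.6.5 makes the same condition: "Where locally available, diffusing capacity of the lungs for carbon monoxide (DLCO) measurements will also be performed".

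SAP 18.2.6 has a pulmonary category of events of special interest with a decreased gas exchange subcategory, and it names DLCO as the measure. It also says that test data will be reviewed for cases investigators may have missed and to supply quantitative data on these events. SAP 18.8.2 flags a fall in DLCO of more than 20% from Baseline as potentially important.

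Protocol 11.9 commits to listing and summarizing all safety data by treatment group and states no minimum count. SAP 3.3 declares no change from the protocol.

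**The concern.** A fixed count of 50 does no harm for a test scheduled in everyone, but it matters for a test whose collection depends on site equipment. DLCO is the only protocol-scheduled PFT measure in that position, and it is also the one attached to a named event of special interest.

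If DLCO falls short of 50 subjects, the plan as written produces no by-arm table of DLCO levels or changes. One primary objective is to select a dose on efficacy and safety. A modest shift in average DLCO at one dose would show in a by-arm table but is hard to see in a subject-level listing. The event table counts reported events, and SAP 18.2.6 itself allows that investigators may not report every case.

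**Working it through.** **Inputs**
- Limit: 50 subjects (SAP 18.8.3 and 18.4.1). It is a bare rule with no stated derivation, so there is no figure to reproduce.
- Planned size: "Approximately 96 subjects are planned to be enrolled" (Protocol synopsis).
- Allocation: 3:3:2 (SAP 3.1).
- DLCO availability, *a*: not in the documents. It is treated as an assumption and shown over a range.

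**Threshold as a share of the trial**

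50 / 96 = 52.1%.

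**Size of what can be left out**

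Planned arms are 96 × 3/8 = 36, 96 × 3/8 = 36 and 96 × 2/8 = 24. The largest DLCO subset that would still be suppressed is 49 subjects. By arm that is 49 × 3/8 ≈ 18, 49 × 3/8 ≈ 18 and 49 × 2/8 ≈ 12.

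**Chance of falling below the limit**

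Let X be the number of the 96 with DLCO, X ~ Binomial(96, *a*). The summary is lost when X ≤ 49.

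| Assumed availability *a* | Expected n = 96*a* | P(X ≤ 49) |
|---|---|---|
| 40% | 38.4 | 0.99 |
| 45% | 43.2 | 0.90 |
| 50% | 48.0 | 0.62 |
| 55% | 52.8 | 0.25 |
| 60% | 57.6 | 0.05 |
| 70% | 67.2 | < 0.001 |

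The model treats subjects as independent. Availability is set by site, so the true spread is wider and the probabilities are less extreme than shown at both ends.

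**Extension Treatment Period**

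SAP 5.7 derives the Safety Set separately for each period, but the rule does not say which set the 50 refers to. If it is applied to the extension set, the DLCO share needed is 50 divided by the number entering. Entry rates are again assumptions:
- 90% entry, 86 subjects: 50/86 = 58%
- 80% entry, 77 subjects: 50/77 = 65%
- 70% entry, 67 subjects: 50/67 = 75%

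The rule also does not say whether the count is per visit or requires a Baseline and post-Baseline pair. Either reading would raise the share needed.

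**Which outputs the limit reaches**

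| Output | Affected if fewer than 50 have DLCO? |
|---|---|
| DLCO value and change from Baseline by visit (SAP 18.8.1) | Yes, lost |
| Incidence of markedly abnormal PFT values (SAP 18.8.1, 18.8.2) | No change for DLCO; its criteria cover only FEV1, FVC and their ratio |
| Table of DLCO falls above 20% (SAP 18.8.2) | None is promised; such values are only to be identified |
| Events of special interest by category and preferred term; exposure-adjusted rates (SAP 18.2.6) | No; the limit covers assessments, not adverse events |
| PFT listings (SAP 18.8.1) | No; all PFT data are listed |

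**The case against.** The strongest reply is that little is lost. The event table, exposure-adjusted rates and listings survive. A second listing covers subjects with any PFT abnormality, and SAP 18.2.6 provides a review of test data for missed cases. SAP 18 plans no statistical safety comparisons unless otherwise specified, so the missing output is one descriptive table. All of this stands. A reader might infer that the limit cancels the special-interest output, a table of the 20% criterion, or a formal pulmonary comparison. The documents support none of these.

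A second reply is that low availability should not be presumed. Protocol 10.6.5 goes on to say that PFTs and DLCO, or other acceptable methods, will be conducted in all subjects. Sites without DLCO must consult the Sponsor, and Appendix 11 requires tests missed under COVID-19 restrictions to be made up. This also stands: a range set wholly below 52% would build the answer into the assumption. But the allowance for other methods and the explicit local-availability condition leave DLCO unguaranteed.

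Third, FEV1, FVC, OCT and the Table 3 safety laboratory panels are scheduled for all subjects and should clear 50 in the double-blind period. That is correct. The rule's wording is general, but its foreseeable effect is on DLCO.

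Fourth, a small subset selected by site equipment may be better listed than summarized. That is a defensible convention, but the limit also suppresses a subset as large as 49, about 18/18/12 by arm, and a footnote can carry the caution.

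Finally, Protocol 11.9 leaves the detail of safety analyses to the SAP. A rule that withholds a summary goes further than detail, however, and SAP 3.3 should say so. Nor is the omission hidden: the rule is written in the SAP, and DLCO is marked as conditional. A reader might call it a silent disappearance, which overstates it.

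**Conclusion.** The concern holds in a limited, conditional form. As written, the SAP can drop the by-arm DLCO value and change-from-Baseline summary, and with it the quantitative group-level view of a measure it names for an event of special interest. Whether that happens depends on DLCO availability, which the documents do not give. The loss is near certain at an assumed 40%, more likely than not at 50%, unlikely at 60% and negligible at 70%. The risk is higher if the 50 is counted on a smaller Extension Safety Set. These figures rest on about 96 subjects and independent availability.

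It would go too far to say that DLCO will be lost, or that laboratory, spirometry and OCT summaries generally are at risk in the double-blind period.

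Two defects do not depend on availability. The limit departs from Protocol 11.9 without being declared in SAP 3.3, and how the 50 is counted is undefined, so two programmers could produce different outputs.

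**What to change.** Before unblinding for the Main Analysis:
- In SAP 18.8.3, and in 18.4.1 for the Protocol Table 3 laboratory tests, exempt protocol-scheduled tests from the 50-subject limit. At minimum exempt DLCO. Summarize them by arm with n shown.
- Add a by-arm count of subjects with a DLCO fall above 20% from Baseline, with the number assessed as denominator. The exemption alone would not create this output.
- Keep the limit only for unscheduled or non-protocol tests, and state whether the 50 is counted overall or per period.
- Declare any limit that remains in SAP 3.3 as a departure from Protocol 11.9.

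The cost is a few edited SAP sentences and some extra tables, with no new data collection. The downside is small-n tables from a subset selected by site equipment; a footnote should say so.
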